3.4.2. Peyronie's Disease

In the clinical studies in subjects with Peyronie's disease, AA4500 was intended to decrease curvature deformity through the injection of collagenase clostridium histolyticum into the pathologic penile plaque, which is composed predominantly of collagen, by disruption of the collagen-rich plaque that causes the curvature deformity.

AA4500 has a consistent safety profile that has been demonstrated among 1044 subjects with Peyronie's disease worldwide. Most adverse events following AA4500 injection were confined locally to the penis or groin and most commonly include penile ecchymosis, penile swelling, and penile pain. Most adverse events following AA4500 injection are mild or moderate in severity and generally resolve prior to the next injection cycle.

In the Peyronie's clinical program, treatment-related SAEs were related to the penis and included corporal rupture (fracture of penis) and penile hematoma.

Data from PK study AUX-CC-805 showed that among evaluable subjects, plasma concentrations for AUX-I and AUX-II were low (ie, maximal concentrations in these subjects: 28.2 ng/mL for AUX-I; 70.8 ng/mL for AUX-II) and transient (ie, detected only through the 0.5 hour post-injection time point) following each injection. No subject had quantifiable plasma levels 15 minutes after modeling of the plaque on Day 3, which suggests that manual modeling of the penis performed 24 hours after the second (Day 2) injection does not result in release of AA4500.

3.5.2. Study AUX-CC-870

Study AUX-CC-870 was a Phase 2a open-label dose ranging study. The objectives of this study were to assess the safety, effectiveness, and immunogenicity of AA4500 in the treatment of AC. To be eligible for treatment, a subject must have had unilateral idiopathic AC of the shoulder with restricted ROM in the affected shoulder for at least 3 months but not more than 12 months. Dosing began with Cohort 1 (0.29 mg/1 mL). Dosing for Cohort 2 (0.58 mg/2 mL), Cohort 3 (0.58 mg/1 mL), and Cohort 4 (0.58 mg/0.5 mL) did not begin until the safety of all subjects in Cohort 1 was evaluated. Subjects assigned to Cohorts 1 through 4 could have received up to three injections of AA4500 separated by a minimum of 21 days. Subjects assigned to Cohort 5 received home shoulder exercises only. A total of 50 adult women and men enrolled in this study.

The primary endpoint was the change from baseline to the Day 92 visit in AROM forward flexion of the affected shoulder. Cohorts 2 and 3 had statistically significant mean increases (37.5° and 42.9°, respectively) in AROM forward flexion from baseline to Day 92 compared to Cohort 5 (12.0°).

For the secondary endpoints, Cohort 3 had statistically significant greater mean increases in AROM abduction, PROM forward flexion, PROM abduction, and PROM external rotation compared to Cohort 5. Cohorts 2 and 3 had statistically significant mean increases (41.6 and 35.9, respectively) in ASES composite score from baseline to Day 92 compared to Cohort 5 (9.9). In addition, Cohorts 2 and 3 had statistically significant mean increases in ASES pain (15.5 for each) and function (26.0 and 19.2, respectively) subscale scores from baseline to Day 92 compared to Cohort 5 (1.5 and 8.4, respectively). Cohorts 2 and 3 had the highest satisfaction rates, with 60.0% and 80.0% of subjects, respectively, very satisfied with treatment at Day 92, compared with 50.0% for Cohort 5. Cohorts 2 and 3 had the highest investigator global assessment of improvement, with 50.0% and 70.0%, respectively, very much improved at Day 92, compared with 20.0% for Cohort 5.

AA4500 was well tolerated in all cohorts. Most subjects in cohorts that received AA4500 had TEAEs that were related to study drug. Common (≥ 2 subjects in any cohort) treatment-related TEAEs were injection site hematoma (all had the verbatim term of bruising), injection site hemorrhage (all had the verbatim term of ecchymosis), injection site pain, injection site swelling, contusion (all had the verbatim term of bruising), musculoskeletal pain, pain in extremity, and ecchymosis. These AEs are expected and consistent with the previous safety profile of AA4500, in which the effects of AA4500 remained localized to the site of injection. No subject died, experienced an SAE, or prematurely discontinued the study or study drug due to AEs. No

clinically meaningful or concerning trends were observed with regard to hematology and chemistry laboratory parameter results, vital sign results, or immunogenicity results.

No clinically significant changes in MRI results from baseline to Day 92 were observed in any cohort. There was no finding suggestive of rotator cuff injury after treatment with AA4500

The efficacy results suggest the clinical effectiveness of AA4500 treatment in Cohort 3 (0.58 mg/1 mL) and Cohort 2 (0.58 mg/2 mL) for the treatment of AC, as shown by statistically significant improvement from baseline to Day 92 in AROM forward flexion compared to Cohort 5 (exercise only). Additionally, subjects in Cohort 3 (0.58 mg/1 mL) had statistically significant improvement from baseline to Day 92 in abduction, external rotation, the ASES pain subscale, the ASES function subscale, and the investigator global assessment of improvement compared with Cohort 5 (exercise only).

Furthermore, the safety results indicate that AA4500 is generally safe and well tolerated, with TEAEs primarily occurring at the site of injection and with a profile consistent with that observed in previous clinical studies with XIAFLEX® in the treatment of Dupuytren's contracture with a palpable cord and Peyronie's disease.

Based on these results, the AA4500 0.58 mg/1 mL dose was selected for further development in the adhesive capsulitis clinical program.

4. STUDY OBJECTIVES

The objectives of this study are to assess the safety, effectiveness, and immunogenicity of AA4500 in the treatment of adhesive capsulitis.

5. INVESTIGATIONAL PLAN

5.1. Overall Study Design and Plan: Description

This study is a Phase 2b, double-blind, placebo-controlled study of the safety and efficacy of AA4500 for the treatment of adhesive capsulitis of the shoulder. To be eligible for treatment, a subject must have unilateral idiopathic adhesive capsulitis of the shoulder with restricted range of motion in the affected shoulder for at least 3 months but not more than 12 months. Subjects will be screened for study eligibility within 28 days before injection of study drug.

Approximately 300 adult women and men are to be enrolled in this study. Following screening and determination of study eligibility, eligible subjects will be randomized 3:1 to receive AA4500 0.58 mg/1 mL or placebo. Subjects will receive up to 3 injections of study drug. Each injection will be separated by a minimum of 21 days. Subjects will also be instructed in home shoulder exercises after the first injection.

Table 1: Study AUX-CC-871 Assessments

Procedures	Screening Day -28 to -1	Injection 1 (Day 1)		Day 8 (± 2 days)	Injection 2 (Day 22) and Injection 3 (Day 43)		Day 29 and Day 50 (±2 days)	Follow-up Day 64 (+7 days)	EOS: Day 95 (± 7 days)/ Early Withdrawal
		Prc- injection	Post- Injection		Prc- injection	Post- Injection			
Obtain informed consent	X								
Medical history/AC history	X								
Prior/concomitant medications/procedures	X	X	X	X	X	X	X	X	X
PE with body weight, height, hand dominance	X								
Vital signs	X	X ^a	X ^a	X	X ^a	X ^a	X	X	X
Targeted examination of the affected shoulder:									
• Inspection, signs of instability and impingement	X ^b								
• AROM and PROM	X ^b	X		X	X	X	X	X	X
• ASES Pain sub-scale	X								
• ASES Function sub-scale	X								
• Pain with movement	X								
12-lead ECG	X								
X-ray of the affected shoulder	X								
MRI of affected shoulder	X								
Clinical laboratories	X								X
Urine pregnancy testing (dipstick)	X	X			X				
Anti-AUX-I/anti-AUX-II antibodies and Nabs	X								X
Randomization		X							
Compliance with home shoulder exercises				X	X	X	X	X	X
Investigator assessment of improvement with treatment									
Subject satisfaction with treatment									
Injection site reactions/local tolerability		X	X	X	X	X	X	X	X
Adverse events	X	X	X	X	X	X	X	X	X
Instructions for home shoulder exercises									
Eligible for retreatment (yes/no)					X ^c				

AROM=active range of motion; PROM=passive range of motion; VAS=visual analogue scale

^a 4 hours before injection and approximately 15, 30 and 45 minutes after injection, and before discharge.

^b The unaffected shoulder will also be examined at screening.

^c Subjects may receive up to a total of three injections; each injection separated by a minimum of 21 days.

NOTE: Subjects who are not eligible for Injection 2 and/or Injection 3 (eg, successfully treated or safety concern) will have follow-up visits on Day 43 and Day 64. Subjects who are not eligible for Injection 2 and/or Injection 3 will not be required to have a study visit on Day 29 and/or Day 50, respectively.

Subjects who are not eligible for Injection 2 because of a safety concern may receive Injection 3 at the discretion of the investigator.

All subjects will have a final follow-up visit on Day 95.

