 - Other significant medical condition (eg, morbid obesity, cervical disc disease), which in the investigator's opinion would make the subject unsuitable for enrollment in the study
4. Is unwilling or unable to cooperate with the requirements of the study including completion of all scheduled study visits.
 5. Has received oral or intravenous steroids for any reason within 3 weeks before the screening visit
 6. Has received an investigational drug or treatment within 30 days before the first dose of study drug.
 7. Has a known allergy to collagenase or any other excipient of AA4500 or any other procedural medication.
 8. Has, at any time, received collagenase for the treatment of adhesive capsulitis.
 9. Is unable to undergo an x-ray or MRI (contraindication) evaluation of the affected shoulder.
 10. Is planning to be treated with commercial XIAFLEX at any time during the study

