6.3. Subject Withdrawal Criteria

Each subject has the right to withdraw from the study at any time without prejudice. If a subject withdraws from the study, the reason(s) must be stated in the subject's medical record and recorded onto the case report form (CRF). A final evaluation of the subject should be performed before discharge.

The investigator may discontinue any subject's participation if he or she feels it is necessary for any reason, including any adverse event, clinically significant adverse change in any laboratory test, or failure to comply with the protocol including the use of anticoagulants or inability to comply with the visit schedule.

Subjects who withdraw from the study or who are discontinued for any reason should have a final evaluation performed either before withdrawal or as soon as possible after discontinuation. Please refer to Day 95/Early Withdrawal on Schedule of Assessments for details (Table 1).

Subjects who withdraw from the study will not be replaced unless it is mutually agreed upon in writing by the respective principal investigator and Auxilium Pharmaceuticals, Inc.'s medical monitor.

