7.7. Care Procedures After Injection

To evaluate the subject for possible immediate immunological adverse events, the subject will remain in direct observation of medical personnel who are skilled in the management of acute allergic reactions for the first 20 minutes after receiving an injection of study drug (see Section 7.6). A subject may be discharged from the study unit after a 45-minute observation period provided:

- The subject exhibits no sign of an immunological or other clinically significant systemic or local adverse event
- The subject's vital signs have remained stable throughout the 45-minute observation period (see Section 7.14.7)

Before discharge, the subject will be instructed to limit movement of his/her treated shoulder for 10 to 12 hours after injection of study drug. The investigator or qualified designee will apply a sling to the treated shoulder within 4 hours after injection. The sling will serve as a reminder to the subject to limit movement of the treated shoulder. Subjects will be instructed to remove the sling before sleeping and to inspect the treated shoulder for edema, sensation, and movement. The subject will be instructed to contact the investigator immediately if any problems are noticed.

Additionally, subjects will be instructed **NOT** to lift or carry any heavy objects for at least 8 weeks after each injection of study drug.

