7.11. Treatment

Subjects may receive up to a maximum of 3 injections of study drug. Each injection will be separated by a minimum of 21 days.

Subjects will receive Injection 1 on Day 1 of the study. Administration of subsequent injections (ie, Injection 2, Injection 3) will be determined by the guidelines outlined in Table 2:

- Do not retreat: Subjects who meet all criteria for ‘do not retreat’ after Injection 1 or Injection 2 will not receive subsequent injection(s).
- Retreat: Subjects who meet all the criteria for ‘retreat’ after Injection 1 or Injection 2 will be eligible to receive subsequent injection(s) provided there are no safety issues (eg, adverse events; allergic reaction), as determined by the investigator.
- Investigator-Discretion: Subjects who do not meet the criteria for ‘do not retreat’ or ‘retreat’ after Injection 1 or Injection 2, will receive additional treatment at the discretion of investigator.

Table 2: Guidelines for Retreatment of Affected Shoulder

	Do Not Retreat^a	Retreat^b
Forward flexion:		
Active (sitting)	≥160°	<140°
Passive (supine)	≥160°	<140°
Abduction:		
Active (sitting)	≥160°	<140°
Passive (supine)	≥160°	<140°
External rotation with the elbow up to 90° abduction:		
Active (sitting)	≥45°	<30°
Passive (supine)	≥45°	<30°
Internal rotation with the elbow up to 90° abduction:		
Active (sitting)	≥45°	<30°
Passive (supine)	≥45°	<30°
^a Do not retreat if all measurements criteria are met. ^b Retreat if all measurement criteria are met and if the investigator determines there are no safety issues (eg, ongoing adverse events).		
IF NEITHER THE CRITERIA FOR 'DO NOT RETREAT' OR 'RETREAT' ARE MET AFTER INJECTION 1 OR INJECTION 2, THEN ADDITIONAL TREATMENT WILL BE AT THE DISCRETION OF INVESTIGATOR.		

7.11.1. Subjects Not Eligible for Injection 2 and/or Injection 3

Subjects who are not eligible for Injection 2 and/or Injection 3 (eg, successfully treated or ongoing adverse events) will have follow-up visits on Day 43 (Section 7.13.5) and Day 64 (Section 7.13.7). Subjects who are not eligible for Injection 2 and/or Injection 3 will not be required to have a study visit on Day 29 and/or Day 50, respectively. Subjects who are not eligible for Injection 2 because of ongoing adverse events may receive Injection 3 at the discretion of the investigator.

All subjects will have a final follow-up visit on Day 95.

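### The Table 1 note permits Injection 3 after Injection 2 was withheld for any safety concern; section 7.11.1 words this more narrowly, and neither excepts an allergic reaction

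*Protocol*

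**What the plan says.** Up to three injections are planned, on Days 1, 22 and 43. Section 7.11 sorts subjects by range of motion into three branches.

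- **Retreat.** Further injections are allowed "provided there are no safety issues (eg, adverse events; allergic reaction), as determined by the investigator". Table 2, footnote b, repeats the condition: "if the investigator determines there are no safety issues (eg, ongoing adverse events").
- **Do not retreat.** No further injection is given.
- **Investigator-Discretion.** Everyone in neither branch "will receive additional treatment at the discretion of investigator". No safety condition is attached here.

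A subject refused Injection 2 may still come back for Injection 3, and this permission is written twice. The note under Table 1 (section 5.1) reads: "Subjects who are not eligible for Injection 2 because of a safety concern may receive Injection 3 at the discretion of the investigator". Section 7.11.1 reads: "Subjects who are not eligible for Injection 2 because of ongoing adverse events may receive Injection 3 at the discretion of the investigator".

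On allergy itself, exclusion criterion 7 (section 6.2) removes a subject who "Has a known allergy to collagenase or any other excipient of AA4500 or any other procedural medication". Section 3.4.1 calls AA4500 a foreign protein, expects antibodies in every treated subject, and records serious allergic reaction with possible anaphylaxis under the marketed product.

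**The concern.** Section 7.11 counts an allergic reaction among the safety issues that withhold an injection. The Table 1 note then reopens the next injection for anyone held back for a safety concern, without qualification. Read together, the two place an allergic subject inside a written permission to be dosed again. The same subject, with the allergy known beforehand, could not have entered the trial.

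What is at stake is the safety of a few subjects exposed again to a foreign protein. The decision would be made blinded, under 3:1 allocation, at about 35 sites. Serum for antibodies is drawn only at screening and Day 95, so no on-treatment antibody result is available to guide the choice on Day 22 or Day 43.

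**Working it through.** The plan states no figure on this point, so the check is mainly a comparison of texts.

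**1. The two permissions.** Both concern the same act, Injection 3 after Injection 2 was refused. They differ in the trigger: any safety concern in the note, ongoing adverse events in 7.11.1. Take a systemic reaction on Day 1 that has settled by Day 22. If the investigator still refuses Injection 2 because of it, the reason is a safety concern but not an ongoing event. The note covers that subject; 7.11.1, read literally, does not. A reaction still present on Day 22 falls under both. Aligning the two phrases therefore narrows the gap but does not close it.

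**2. Provisions that could stop the dose.**

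| Provision | What it does | Ends dosing after a related systemic reaction? |
|---|---|---|
| 7.11, Retreat bullet | Names allergic reaction as a safety issue | Only as the investigator determines, and only in this branch |
| Table 2, footnote b | Repeats the no-safety-issues condition | Same limits |
| 7.11, Investigator-Discretion bullet | Leaves treatment to discretion | No safety condition stated |
| 6.2, criterion 7 | Bars known allergy | Listed under selection; not repeated among the checks in 7.13.5.1 |
| 7.13.5.1 | Investigator must deem the subject eligible | Discretionary |
| 6.3 | Investigator may end "participation if he or she feels it is necessary for any reason, including any adverse event" | Discretionary |
| 7.7 | Discharge requires: "The subject exhibits no sign of an immunological or other clinically significant systemic or local adverse event" | Governs discharge that day, not the next dose |

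No row gives a definite stop.

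**3. Reach of the branch without a proviso.** The Retreat and Do-not-retreat branches each require all eight measurements in Table 2 (four planes, active and passive) to pass the threshold. Any mixed or intermediate result goes to Investigator-Discretion. That branch also covers a subject who reacts to Injection 2 and is being considered for Injection 3, a case the 7.11.1 permission does not address.

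**4. Cost of a stop, as an upper bound.** From section 10.3, 225 AA4500 subjects are planned, with at most 3 injections each: 3 × 225 = 675 injections, of which 2 × 225 = 450 are re-injections. Let p be the proportion with a related systemic reaction. If all react to Injection 1 and would otherwise have received both later injections, the number forgone is at most 450 × p. The documents give no p, so the range is assumed:

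- p = 0.002: 0.9 forgone (0.9/675 = 0.13%)
- p = 0.005: 2.25 forgone (0.33%)
- p = 0.01: 4.5 forgone (0.67%)

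Some of these injections would be withheld anyway under 7.11, so the true cost is lower for a given p. The results appended to the Protocol do not fix p. They list no allergic reaction among serious events on AA4500 (0/237; one-sided 95% upper limit 1 − 0.05^(1/237) = 1.3%), but non-serious terms below 5% are not shown. Pruritus was reported in 12/237 on AA4500 and 0/84 on placebo, with the site not stated. If all 12 were systemic and related after Injection 1, the ceiling would be 450 × 12/237 = 22.8 injections (3.4%). Isolated local pruritus would not count under the rule proposed.

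**The case against.** The strongest reply is that this is drafting, not a flaw. The two sentences are parallel, the note summarizes the section, and its broader term is probably table shorthand for the same temporary events. Allergy is already named in 7.11 as a reason to withhold subsequent injections, which includes the third. A branch that rests on the investigator's judgement hardly needs a reminder to consider safety. Criterion 7 may be read as continuing through the study. The Investigator's Brochure, which is not shown, may give guidance on dosing after hypersensitivity.

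Much of this stands. The likely intent is benign, and a careful investigator would probably stop. A reader might infer that the Protocol directs re-injection of allergic subjects, or that the note and 7.11.1 contradict each other outright. The documents support neither: both texts only permit, and one is broader than the other.

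What the reply leaves untouched is that a written permission reaches a subject with an allergic reaction and no written exception takes that subject out. Each safeguard cited depends on discretion or applies to a different moment.

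A reader might also want a wider stop, covering any reaction not clearly unrelated to study drug or caused by any procedural agent. The Protocol does not support that. Section 8.3 has two causality categories, Related and Not related, and no third. Section 7.5 names chlorhexidine and Betadine as examples of antiseptics and does not fix the anesthetic, so a reaction to one of these agents can be met by replacing it.

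**Conclusion.** The point holds as a minor subject-safety improvement. The permission for Injection 3 is worded more broadly in the Table 1 note than in 7.11.1, and neither place excepts an allergic reaction. The Retreat proviso, footnote b, 7.13.5.1 and 6.3 give real but discretionary protection.

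The number of subjects who would be re-exposed cannot be derived from the documents, and none is claimed. A reader might infer that the gap distorts the efficacy result; nothing here bears on the Day 95 comparison, its power or its error rate. The conclusion assumes that the sections not shown and the Investigator's Brochure contain no dosing stop. The appended results show that the trial has been completed, so the practical value lies in any later protocol that reuses this wording.

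**What to change.** 1. In the Table 1 note, use the narrower trigger of 7.11.1, ongoing adverse events.
2. In 7.11, apply the no-safety-issues proviso to the Investigator-Discretion branch as well as to Retreat.
3. In 7.11, 7.11.1 and the Table 1 note, state that a systemic allergic or hypersensitivity reaction assessed as Related to study drug under 8.3 ends study-drug dosing, with follow-up to Day 95.
4. State that local injection-site reactions do not count, and that a reaction attributed to a replaceable antiseptic or local anesthetic stays at the investigator's discretion, with that agent replaced.

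This needs protocol wording and a notice to sites, with no extra visit, test or subject. The causality judgement in 8.3 can be made without unblinding. The price is some loss of investigator discretion and a small number of forgone injections that cannot be firmly estimated: under 1% of planned AA4500 injections across the assumed range of 0.2% to 1%.
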